### Study Design: Biomedical

#### 1. Will controls be used?

Answer/Response: Yes

##### ► IF YES, explain the kind of controls to be used.

Answer/Response: active comparator

#### 2. What is the study design?

Example: case series, case control study, cohort study, randomized control study, single-blind, double-blind, met-analysis, systematic reviews, other. You may also view the IRB-HSR Learning Shot on this topic to help you answer this question.

[http://www.virginia.edu/vpr/irb/learningshots/Writing\\_protocol\\_June09/player.html](http://www.virginia.edu/vpr/irb/learningshots/Writing_protocol_June09/player.html)

Answer/Response: this will be a single-center, prospective, randomized, active-control study in pediatric (age < 24 months) patients undergoing elective cardiac surgery with CPB in-whom fibrinogen supplementation after separation from CPB is indicated, based on the presence of clinically-significant bleeding and documentation of low fibrinogen level on viscoelastic point-of-care testing (MCF < 10 mm on the FIBTEM assay of ROTEM)

**3. Does the study involve a placebo?**

Answer/Response: No

► **IF YES, provide a justification for the use of a placebo**

Answer/Response:

### Human Participants

**Ages:** \_\_under 24 months of age\_\_

**Sex:** \_\_male or female\_\_

**Race:** \_\_any\_\_

**Subjects-** see below

**INSTRUCTIONS:** For question 1-4 below insert an exact #. Ranges or OPEN is not allowed. This # should be the maximum # you expect to need to enroll (i.e. sign consent) If you are only collecting specimens the number of participants should equate to the # of specimens you need. If you are collecting only data from a chart review the number should designate the number of subjects whose medical records you plan to review. Age/ Sex/Race criteria should designate the demographics of participants from whom you will obtain the specimen/data.

**1. Provide target # of subjects (at all sites) needed to complete protocol.**

**INSTRUCTIONS:** If this is NOT a database protocol, this number should be the same as the number of subjects needed to obtain statistically significant results.

Answer/Response: 30 total with 15 in each arm

**2. Describe expected rate of screen failure/ dropouts/withdrawals from all sites.**

Answer/Response: 5%

**3. How many subjects will be enrolled at all sites?**

**INSTRUCTIONS:** This number must be the same or higher than the # from question # 1 in order to account for the # of screen failures, dropouts, withdrawals described in question # 2.

Answer/Response: 32

**4. How many subjects will sign a consent form under this UVa protocol?**

**INSTRUCTIONS:** If the protocol does not have a consent form- the number listed here should reflect such things as the number of subjects from whom specimens will be obtained, the number of charts to be reviewed etc.

Answer/Response: 32

### Inclusion/Exclusion Criteria

**INSTRUCTIONS:**

- The inclusion and exclusion criteria should be written in bullet format.
- *This item applicable if the study will require consent (verbal or written).* Unless there is a scientific reason for not recruiting a certain type of vulnerable population(e.g. not

enrolling fetuses, neonates or children in a study regarding Alzheimer's) list the following vulnerable populations under either Inclusion or Exclusion criteria below: pregnant women, fetuses, neonates, children, prisoners, cognitively impaired, educational or economically disadvantage, non- English speaking subjects .

- If you will not enroll subjects who do not speak English because certain procedures cannot be carried out if the subject does not speak English (e.g. a survey is not validated in other languages) insert the following as an Inclusion Criteria: Willingness and ability to comply with scheduled visits and study procedures.
- If this is a collection of only retrospective\* specimens or data, the inclusion criteria must include a start and stop date for when specimens/ data will be collected.
- The stop date must be prior to the version date of this protocol.
- \*Retrospective: all specimens are in a lab at the time this protocol is approved by the IRB. All data exists in medical records or records from previous studies at the time this protocol is approved by the IRB.

**1. List the criteria for inclusion**

Answer/Response:

- pediatric (age < 24 months) patients undergoing elective cardiac surgery with CPB in-whom fibrinogen supplementation after separation from CPB is indicated, based on the presence of clinically-significant bleeding and documentation of low fibrinogen level on viscoelastic point-of-care testing (MCF < 10 mm on the FIBTEM assay of ROTEM).

**2. List the criteria for exclusion**

Answer/Response:

- refusal to participate in the study,
- known severe allergic reaction/anaphylaxis to fibrinogen concentrate,
- administration of FC or cryoprecipitate in the 24 hours prior to surgery and
- baseline fibrinogen level higher than 300 mg/dL (to avoid the risk of increasing the fibrinogen level above the normal upper level of 400 mg/dL)

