**3. List any restrictions on use of other drugs or treatments.**

Answer/Response: None

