**INSTRUCTIONS:**

The stratification factors and/or the randomization plan should be identified. If there is no randomization component or important patient characteristics that will be used in treatment allocation or data analysis, a statement to this effect should be included.

Stratification factors: These are pretreatment patient characteristics which could be balanced across treatment arms by design or may be used to determine starting dose or treatment allocation.

If randomization is going to be used, the details of the randomization plan should be described.

The description should include:

- the method and timing of randomization
- the type of randomization scheme that will be used in the study
- whether or not the randomization masked/blinded/if so, then to whom is it masked/blinded
- who has access to the randomization scheme

Answer/Response:

- Once the need for fibrinogen supplementation is confirmed after separation from CPB, patients will be randomized into one of two treatment groups (n=15 in each group):
  1. Cryoprecipitate group (dose: 10 ml/kg; active control group) or
  2. Fibrinogen Concentrate group (dose: 70 mg/kg; intervention group).
- 1:1 randomization unblinded using a computer generated randomization list

► IF YES, who will generate the randomization scheme?

\_\_\_\_\_ Sponsor

\_\_\_\_\_ UVa Statistician.  Insert name Answer/Response:

\_\_\_\_\_ UVa Investigational Drug Service (IDS)

\_\_x\_\_ Other:  Specify Answer/Response: computer generated by the CRC

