In the event that a second round of fibrinogen supplementation is required (bleeding with documented hypofibrinogenemia) participants will receive either FC or cryoprecipitate based on their initial randomization. If any additional fibrinogen supplementation is then needed (after the first 2 supplementation doses), cryoprecipitate will be administered to all subjects per standard of care (including those who received FC).

Data to be obtained:

1. Demographic/preoperative data: collected from the medical record
  - age in days/months (all patients to be younger than 24 months)
  - gender
  - weight
  - preoperative diagnosis
  - surgery type & date (Norwood, arterial switch, truncus arteriosus, Glenn, Fontan, TAPVR, AV canal, tetralogy of Fallot, etc)
  - preoperative standard of care labs PT/aPTT/INR/hgb level/ hematocrit/ platelet count/

fibrinogen level (if exists)/ creatinine

2. Intra-operative Data: collected from the medical record

- CPB time & aortic cross clamp time
- use of hypothermic circulatory arrest (ice packs placed on the head)
- was post-CPB ultrafiltration performed?
- Platelet count prior to separation from CPB
- was ATIII administered? (thrombate)
- Transfusion requirements: PRBC/Cell Saver/FFP/PLT/ cryo - to be collected as number of units per each product, not volume. (for PLT - was it pooled PLT or single donor apheresis, if possible)
- was rFVIIa given (factor seven, novoseven). Please pay attention - the fact that rFVIIa was ordered DOES NOT mean that was actually administered as we order factor VII for ALL big cases (to have available in the OR) but not necessarily administer it
- Need for ECMO
- Was the chest left open? (always in ECMO, but open chest does not necessarily mean ECMO)

ROTEM (clotting labs) will be drawn for research purposes after admission and after administration of the study treatment: Extem (CT/A10/A20/MCF); Fibtem (A10/A20/MCF) and fibrinogen. The blood drawn for this will be obtained through an existing line, put into place as part of the subject's usual care.

3. Postoperative Data (PICU, up to 48 hours after surgery) collected from the medical record

- admission PT/aPTT/INR/platelet count/ fibrinogen level/ hgb level/HCT level (could be obtained from initial ABG)
- Bleeding (Chest drain/s output)

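### The severe-allergy exclusion names only fibrinogen concentrate, although cryoprecipitate is the other randomised product (a minor eligibility and safety inconsistency)

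*Combined protocol and SAP*

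**What the plan says.** Inclusion/Exclusion Criteria, item 2, has four exclusions: refusal, an allergy criterion, recent exposure, and a baseline fibrinogen above 300 mg/dL. The allergy criterion is "known severe allergic reaction/anaphylaxis to fibrinogen concentrate". The exposure criterion that follows it is "administration of FC or cryoprecipitate in the 24 hours prior to surgery and" (the last word leads into the next bullet).

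The inclusion criterion in item 1 requires age under 24 months, elective surgery on bypass, and an indication for fibrinogen "based on the presence of clinically-significant bleeding and documentation of low fibrinogen level on viscoelastic point-of-care testing". It sets no allergy condition. Item 3, on restrictions on other drugs or treatments, has "Answer/Response: None".

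Human Participants, item 1, sets the target at "30 total with 15 in each arm". Statistical Considerations, item 1, gives "1:1 randomization unblinded using a computer generated randomization list" and defines one arm as "Cryoprecipitate group (dose: 10 ml/kg; active control group"). Study Procedures, item 1, repeats the two arms and keeps a second supplementation on the product first assigned. For any supplementation after two doses it states that "cryoprecipitate will be administered to all subjects per standard of care (including those who received FC").

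**The concern.** Entry to a two-arm comparison of active products normally presumes that a child can receive either one. Here the list screens for a known severe reaction to one product and not to the other. Read literally, it admits a child for whom one of the two possible assignments is known in advance to be unsuitable.

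What is at stake is mainly the safety of an individual child. Consent is taken before surgery, but randomisation happens later, in the operating room or intensive care unit, once the need for fibrinogen is confirmed. If the eligibility list does not settle the matter beforehand, it has to be settled while the child is bleeding.

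**Working it through.** There is no sample-size or error-rate figure to reproduce. The check is a comparison of sections plus one proportion.

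1. **Is a severe reaction to cryoprecipitate excluded anywhere?** Each criterion in turn:
   - Refusal: not relevant to allergy.
   - Allergy: names fibrinogen concentrate only.
   - Exposure in the day before surgery: names cryoprecipitate, but concerns recent administration and not a past reaction.
   - Baseline fibrinogen above 300 mg/dL: a laboratory limit.
   - Inclusion criterion: age, surgery, bleeding and the FIBTEM result.
   - Restrictions on other treatments: none.

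   None of these excludes the child in question.

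2. **Could the wording cover cryoprecipitate by implication?** No. The Background describes two different preparations. Fibrinogen concentrate is purified and pathogen-reduced; cryoprecipitate is not pathogen-reduced and carries several further clotting proteins and platelet microparticles. A history of reacting to one is not the same as a history of reacting to the other.

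3. **Where does the trial itself assign cryoprecipitate?** In the control arm at the first dose, and at the second dose for a child in that arm. Both follow from the randomisation list. From the third supplementation onward, all children receive it under standard care.

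4. **Chance of assignment.** Inputs: 30 children, 15 per arm, 1:1. Probability of cryoprecipitate for a randomised child = 15/30 = 50%. This applies at randomisation, not at consent, because a consented child who never needs fibrinogen is not randomised.

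5. **Expected number affected.** If a proportion p of randomised children had such a history, the expected number assigned cryoprecipitate would be 30 × p × 0.5 = 15p. The documents give no value for p, so this cannot be taken further.

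**The case against.** The strongest reply is that cryoprecipitate is the standard product, so an allergy to it must be managed whether or not the child is in the trial, and the protocol needs to screen only for the product it introduces. Part of this stands. Use from the third supplementation onward is expressly standard care, so it should not be counted as an added trial risk for the fibrinogen concentrate arm. The reply does not cover the first two doses. The Background says the centre has approved fibrinogen concentrate as an alternative for bleeding paediatric surgical patients. Outside the trial a clinician can therefore choose between the products; inside it, the list chooses.

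A second reply is that a known severe reaction would be on the chart and the team would not enrol the child. That is plausible, but the protocol does not say so.

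A reader might also infer a bias. Staff would override a cryoprecipitate assignment and give fibrinogen concentrate, never the reverse, and under intention to treat this would make the arms look more alike. The documents do not support this. They describe no override and give no frequency, and a child who is simply not enrolled causes no crossover.

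**Conclusion.** The point holds as a minor eligibility and safety inconsistency. Followed exactly, the exclusion list admits an otherwise eligible child with a known severe reaction to cryoprecipitate, and that child has a 50% chance of being assigned it if randomised. The conclusion rests on the inclusion and exclusion lists as they stand and on 1:1 allocation.

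Its practical size is unknown and probably very small. A rare history would have to coincide with consent, significant bleeding, a low FIBTEM result and allocation to the control arm. Sample size, power, type I error and the primary analysis do not change.

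A reader might go further and conclude that the exclusion should reach all plasma-derived components. The inconsistency does not require that. It concerns the two randomised products only, and reactions to products that are not randomised are a matter of general care.

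**What to change.** Reconcile the exclusion list (Inclusion/Exclusion Criteria, item 2) with the arms in Statistical Considerations, item 1, and Study Procedures, item 1, so that the known-severe-allergy criterion covers both randomised products, fibrinogen concentrate or cryoprecipitate. The neighbouring exposure criterion already names both and can serve as the model for the wording.

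The cost is a few words in the protocol and a check of the medical record before surgery, which the study already consults for preoperative data. The downside is the possible loss of a very small number of otherwise eligible children. No change to the sample size or the analysis is needed.

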**3. List any restrictions on use of other drugs or treatments.**

Answer/Response: None

## Statistical Considerations

**1. Is stratification/randomization involved?**

Answer/Response: Yes

► IF YES, describe the stratification/ randomization scheme.

**INSTRUCTIONS:**

The stratification factors and/or the randomization plan should be identified. If there is no randomization component or important patient characteristics that will be used in treatment allocation or data analysis, a statement to this effect should be included.

Stratification factors: These are pretreatment patient characteristics which could be balanced across treatment arms by design or may be used to determine starting dose or treatment allocation.

If randomization is going to be used, the details of the randomization plan should be described.

The description should include:

- the method and timing of randomization
- the type of randomization scheme that will be used in the study
- whether or not the randomization masked/blinded/if so, then to whom is it masked/blinded
- who has access to the randomization scheme

Answer/Response:

- Once the need for fibrinogen supplementation is confirmed after separation from CPB, patients will be randomized into one of two treatment groups (n=15 in each group):
  1. Cryoprecipitate group (dose: 10 ml/kg; active control group) or
  2. Fibrinogen Concentrate group (dose: 70 mg/kg; intervention group).
- 1:1 randomization unblinded using a computer generated randomization list

► IF YES, who will generate the randomization scheme?

\_\_\_\_\_ Sponsor

\_\_\_\_\_ UVa Statistician.  Insert name Answer/Response:

\_\_\_\_\_ UVa Investigational Drug Service (IDS)

\_\_x\_\_ Other:  Specify Answer/Response: computer generated by the CRC

**2. What are the statistical considerations for the protocol?**

The objectives section and the statistical section should correspond, and any objective for which analysis is unfeasible should be deleted. Also, the estimates and non-statistical assumptions of the statistical section should be supported by discussion in the background section.

The answer to this question should include:

- Study Design/Endpoints
- Recap of study objectives and endpoint definitions. An assessment of how study objectives will be assessed by identifying & defining which endpoints will be used to assess each component of the study objectives.
- The study design should include contingencies for early stopping, interim analyses, stratification factors (If applicable), and any characteristics to be incorporated in analyses.
- The power/precision of the study to address the major study endpoint(s), the assumptions involved in the determination of power/precision.

--If statistical hypothesis testing is included then specify the null and alternative hypotheses, the test statistic, and the type I and II error rates  
--If precision of an estimate, then provide a definition for precision  
--If other, then specify

Answer/Response: Baseline clinical and demographic characteristics, follow-up measures, and clinical outcomes will be compared on an intention-to-treat basis according to the randomized study group assignment. Continuous variables will be compared using the Student *t* test for normally distributed variables or the Mann-Whitney *U* test or Wilcoxon matched-pairs signed-rank test for non-normally distributed variables. Categorical variables will be compared using the Pearson  $\chi^2$  test or Fisher exact test as appropriate. We estimate that 30 patients would be needed (15 in each study arm) to determine that an exposure to 2 additional allogeneic blood products will be statistically significant (C.I. 95%) providing 80% power with a type I error probability  $\alpha = 0.05$  (including 20% dropouts/withdrawals from the study)

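### A matched-pairs test is listed for comparing two unmatched arms; adjusting for baseline data and indexing drain output to weight would be inexpensive improvements

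*Combined protocol and SAP*

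**What the plan says.** - **Comparison.** Statistical Considerations, question 2, says that "clinical outcomes will be compared on an intention-to-treat basis according to the randomized study group assignment".
- **Tests.** For continuous data the same answer gives the t test if normal and otherwise Mann-Whitney or the "Wilcoxon matched-pairs signed-rank test for non-normally distributed variables". Categorical data get chi-square or Fisher. Every listed test is unadjusted, and nothing says when the signed-rank test would be chosen over Mann-Whitney.
- **Design.** Question 1 of that section specifies "1:1 randomization unblinded using a computer generated randomization list". It describes no matching, pairing or stratification.
- **Data held.** Study Procedures, question 1, collects age, weight and, among the intra-operative items, "CPB time & aortic cross clamp time". Transfusions are recorded as units. ROTEM is drawn for research, including after study treatment.
- **Bleeding.** Question 5 defines it as cell saver volume and chest-drain output over 48 hours. It states no unit and no indexing to weight. Eligible children run from birth to under 24 months.
- **Primary outcome.** Question 4 words it as whether any allogeneic transfusion occurs within 24 hours of treatment, and names no test. Question 2 sizes the trial on a difference of two products.

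**The concern.** A signed-rank test works on differences within pairs. Here infant 1 in one arm has no partner in the other, so the analyst would have to invent the pairs. Two consequences follow. The p-value would depend on that choice, which is left open in an unblinded trial. And the test needs equal numbers, so any imbalance between arms means discarding randomised infants, against the stated intention-to-treat basis. Unit counts, drain output and length of stay are likely to be skewed, so the non-normal branch is the one likely to be used.

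A second, lesser matter is precision. With about 30 infants of very different sizes, the plan makes no stated use of weight or bypass time, both already collected, and does not say whether blood loss is scaled to the child. It also plans no interval for a treatment effect: a 95% CI is mentioned only in the sample-size sentence.

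**Working it through.** **1. The plan's own figure.** Question 2 gives 30 infants for a difference of 2 products, "providing 80% power with a type I error probability" of 0.05, "including 20% dropouts/withdrawals from the study". No SD is stated; two-sided testing is assumed here. Working backwards, 30 × 0.8 = 24 evaluable, or 12 per arm. From n = 2 × (1.96 + 0.842)² × SD² / 2² = 3.92 × SD², setting n = 12 gives SD = 1.75 products (1.67 with the noncentral t). So 30 cannot be derived from the documents, and the SD is an assumption in all that follows.

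**2. The signed-rank test on unmatched arms.**
- With 15 per arm there are 15! possible pairings, about 1.3 × 10¹², and the plan selects none.
- In one simulated 15 versus 15 data set, 5,000 random pairings gave p from 0.21 to 1.00; Mann-Whitney gave 0.93. In a constructed count example, 3,000 pairings gave p from 0.0012 to 0.137 (median 0.027); Mann-Whitney gave 0.020. In the second case the pairing decides which side of 0.05 the result falls.
- Over 6,000 simulated trials of 15 per arm:

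| Data | Quantity | Mann-Whitney | Signed-rank, pairing made without regard to outcome | Signed-rank, values sorted and then paired |
|---|---|---|---|---|
| Normal | Type I error | 4.2% | 4.4% | 57% |
| Lognormal | Type I error | 4.5% | 5.0% | 54% |
| Normal | Power at 1.06 SD | 77% | 75% | not meaningful |
| Lognormal | Power at 1.06 SD (log scale) | 76% | 70% | not meaningful |

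- Unequal arms: if the 20% dropout (6 of 30) fell 4 and 2, arms of 11 and 13 would remain. Only 11 pairs could be formed, and 2 evaluable infants would be discarded.

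**3. What adjustment could gain or lose** (continuous outcomes only). With N infants in total and k covariates explaining a share R² of the variance, adjusted over unadjusted variance is (1 − R²) × (1 + k/(N − k − 3)).
- N = 30, k = 2: the factor is 27/25. At R² = 0.2 the ratio is 0.864 (SE × 0.930); at R² = 0.5 it is 0.540 (SE × 0.735). Break-even is R² = 2/27 = 7.4%.
- N = 30, k = 1: the factor is 27/26, with break-even at 1/27 = 3.7%.
- N = 24, k = 2: the factor is 21/19, with break-even at 2/21 = 9.5%.
- Change in 95% CI width at 15 per arm, including the t quantile:

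| R² (assumed) | 1 covariate | 2 covariates | 3 covariates |
|---|---|---|---|
| 0 | +2% | +4% | +7% |
| 0.1 | −3% | −1% | +1% |
| 0.25 | −12% | −10% | −8% |
| 0.5 | −28% | −26% | −25% |

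The unadjusted half-width is 0.748 SD at 15 per arm. That is 1.3 products at SD 1.75 and 2.2 at SD 3.

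**4. Drain output.** If loss per kg is independent of weight, the log-scale variance of mL over that of mL/kg is 1 + ln(1 + CVw²)/ln(1 + CVr²), where CVw is the coefficient of variation of weight and CVr that of loss per kg. With CVw of 30–50% and CVr of 50–70% (both assumed), this runs from 1 + 0.086/0.399 = 1.22 to 1 + 0.223/0.223 = 2.00. If smaller infants lose more per kg, the ratio falls and could drop below 1.

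**The case against.** The best defence is that the signed-rank test was meant for change within an infant, such as ROTEM before and after treatment, and that Mann-Whitney, listed first, would be used between arms. That may be the intention, but the text does not say so, and the opening sentence of the answer concerns comparison by randomised group.

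Other parts of the defence stand and limit the point:
- A reader might infer that the signed-rank test could give almost any answer. The table does not support that. A pairing made without regard to outcome keeps type I error near 5%, with some loss of power. The gross inflation needs pairing after sorting, which nobody proposes.
- A reader might infer that the plan's intervals are needlessly wide. No effect interval is planned, no SD or R² is given, and an unadjusted comparison of randomised arms is valid. Adjustment is an improvement, not the correction of an error.
- A reader might infer that drain output will be compared in raw millilitres. The plan states no unit; the fair statement is that indexing is unspecified.
- A reader might infer that the research ROTEM goes unanalysed. Question 2 refers generally to follow-up measures, which can include it; it is simply not a named outcome.
- It is tempting to prescribe a linear model of product counts as the primary analysis. That would replace a primary outcome which, in question 4, reads as binary. On that reading chi-square or Fisher applies, and neither the signed-rank problem nor the precision figures touch the primary comparison.

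**Conclusion.** The listing of a matched-pairs test for between-arm comparison is wrong as written. This follows from the plan's own text and needs no assumption. Its practical size is an undefined p-value and possible loss of infants from the analysis, not a demonstrated false-positive problem.

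Covariate adjustment and mL/kg are worthwhile but optional. At 15 per arm with one or two covariates, the change in interval width runs from about 4% wider to about 28% narrower, for R² between 0 and 0.5. That range is assumed, applies to continuous outcomes and is only approximate for counts. The advantage of mL/kg rests likewise on assumed variation in weight and loss, and on loss per kg not rising steeply in smaller infants.

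**What to change.** 1. In question 2, remove the signed-rank test from the between-arm tests and name Mann-Whitney for non-normal variables. If signed-rank is kept, restrict it to named before/after comparisons within an infant, such as FIBTEM, and list the qualifying pre-treatment value as a data item, since the data list does not clearly include it.
2. Reconcile questions 2 and 4 on whether the primary outcome is a count of products or any transfusion, and then name the one primary analysis that suits it.
3. For continuous or count outcomes, pre-specify an effect estimate with 95% CI, adjusted for one or two baseline variables (for example weight, and bypass time up to randomisation). Keep it to two at this sample size.
4. State chest-drain output in mL/kg.

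Cost: plan wording and one or two degrees of freedom, with slightly wider intervals if the covariates prove not to be prognostic. Apart from possibly recording the qualifying FIBTEM value, which eligibility already requires, no new data are needed.

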### **3. Provide a justification for the sample size used in this protocol.**

Include sample size calculations or statistical power estimation. If not applicable, please provide explanation.  
Also include the anticipated accrual rate, the accrual goal for the study, including accrual goals by strata if appropriate, adjustments for drop-outs etc. and study duration.

Answer/Response: This is a pilot study and no power analysis was performed. We anticipate enrollment in 2 years.

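### The protocol claims 80% power for 30 patients, then says no power analysis was done; the figure cannot be reproduced, and 30 means different things in different sections

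*Combined protocol and SAP*

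**What the plan says.** Three places in the protocol bear on the sample size.

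- **Statistical Considerations, question 2** (statistical considerations): "We estimate that 30 patients would be needed (15 in each study arm) to determine that an exposure to 2 additional allogeneic blood products" will reach statistical significance, "providing 80% power with a type I error probability" of 0.05. A closing parenthesis adds that the 30 is stated "including 20% dropouts/withdrawals from the study".
- **Statistical Considerations, question 3** (justification of sample size): "This is a pilot study and no power analysis was performed".
- **Human Participants, questions 1 to 4**: the number needed to complete the protocol is "30 total with 15 in each arm". The expected rate of screen failure, dropout and withdrawal combined is 5%. The number enrolled, and the number signing consent, is 32.

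No section gives an SD for the number of products, a control-arm mean, a transfusion rate, the sidedness of the test, the test behind the 80%, or a source for the calculation. The Background section supplies none of these either.

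**The concern.** Two consecutive answers in the same section cannot both be true: either a power calculation was done or it was not. The 80% is the only operating characteristic that the plan states, and the answer meant to justify the sample size disowns it.

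This affects how the result will be read. The hypothesis is that fibrinogen concentrate is as effective as cryoprecipitate, and no margin is set, so a non-significant difference is the result most likely to be taken as support. A stated 80% power would make that result look informative when nothing in the documents shows that it would be.

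The second problem is the number of patients analysed. If 30 is the count before losses, the analysis rests on 24. If it is the count after losses, it rests on 30. Any power or precision statement depends on which is meant.

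**Working it through.** **Inputs from the protocol.** Difference of 2 products, alpha 0.05, power 80%, 1:1 allocation, 30 patients, 20% loss (Statistical Considerations, question 2); 30 completers, 5% combined loss, 32 enrolled (Human Participants).

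**Inputs not in the protocol.** The SD is missing, so the stated power cannot be reproduced. Below I assume a count outcome with equal SDs in the two arms and a two-sided t-test. The SD values are assumptions that show a range; they are not estimates for this population.

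**Step 1. What 30 means.**
- Question 2: 30 × (1 − 0.20) = 24 evaluable, or 12 per arm. In reverse, 24/0.80 = 30.
- Human Participants: 30/(1 − 0.05) = 31.6, rounded up to 32 enrolled, with 30 completing (15 per arm).
- Cross-check: 32 × 0.80 = 25.6, so a 20% loss from 32 leaves about 26 and not 30. Thirty completers at 20% loss would need 30/0.80 = 37.5, so 38 enrolled.

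Each sum works in its own place. Together they disagree on whether 30 is the number before or after losses.

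**Step 2. The SD at which 80% power would hold.** The standardised difference giving 80% power is 1.197 with 12 per arm and 1.060 with 15 per arm.
- 12 per arm: SD = 2/1.197 = 1.67
- 15 per arm: SD = 2/1.060 = 1.89

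The normal approximation gives 1.75 and 1.96. A one-sided t-test gives 1.91 and 2.15.

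**Step 3. Power over assumed SDs.** The noncentrality is 2/(SD × √(2/n)), with 2n − 2 degrees of freedom. For example, with n = 12 and SD 2 it is 2/(2 × 0.408) = 2.45, giving power 0.649.

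| Assumed SD (products) | Power, 12 per arm | Power, 15 per arm |
|---|---|---|
| 1.5 | 88% | 94% |
| 2 | 65% | 75% |
| 3 | 35% | 42% |
| 4 | 22% | 26% |

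**Step 4. Precision, which can be stated without a power claim.** For a count outcome, the 95% CI half-width for the mean difference is t(0.975, 2n − 2) × √(2/n) × SD.
- 15 per arm: 2.048 × 0.365 × SD = 0.75 SD
- 12 per arm: 2.074 × 0.408 × SD = 0.85 SD

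For a binary outcome, the simple large-sample half-width is 1.96 × √[p1(1 − p1)/n + p2(1 − p2)/n]. It is widest when both proportions are 0.5.
- 15 per arm: 1.96 × √(0.5/15) = 0.36
- 12 per arm: 1.96 × √(0.5/12) = 0.40

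**The case against.** **The power may be adequate.** A reader might infer from the table that the trial is underpowered, or that 80% needs an implausibly small SD. The documents support neither reading. They give no SD, so nothing shows that 1.67 or 1.89 products is small for this outcome, and at SD 1.5 power exceeds the claim. The test and sidedness are also unstated, and a one-sided test would relax the limits. This part of the objection stands in full: the 80% is unsupported, not shown to be too low.

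**The two loss rates may have different denominators.** Consent is taken before surgery, and randomisation follows only once the need for fibrinogen is confirmed. The 5% includes screen failures and is applied to patients consented; the 20% covers dropouts and withdrawals only. One could picture 32 consented, 30 randomised and 24 evaluable. It would therefore be too strong to read 5% against 20% as two values of one rate. The conflict still remains, because Human Participants names dropouts and withdrawals within its 5% and describes the 30 as the number needed to complete.

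**This is a pilot.** A pilot needs no power calculation, and question 3 says none was done, which limits the risk of misreading. That supports keeping question 3. It does not support leaving the 80% in question 2.

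**There is no arithmetic slip.** That is correct. The fault is a contradiction and a missing input; each stated sum is right on its own terms.

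**Conclusion.** The point holds as a contradiction and an unsupported figure. The 80% power in question 2 is denied by question 3, and no reader can recompute it from what the protocol gives. The evaluable number is 24 or 30 depending on the section.

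The two contradictions rest on the protocol's own text and need no outside assumption. The illustrated sizes do depend on the assumed SDs, a count outcome, equal SDs and a two-sided t-test. They show only that the true power could lie well above or well below 80%.

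It is also unsettled whether the power sentence concerns the primary endpoint. That sentence is about a number of products, whereas question 4 words the primary outcome as any allogeneic transfusion within 24 hours, which can be read as yes/no. Any replacement statement has to match the outcome as finally defined.

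**What to change.** 1. Delete the 80% power sentence from Statistical Considerations, question 2, and keep the pilot statement in question 3. If a calculation was in fact done, correct question 3 instead and give the SD actually used, its source, the test and the sidedness. An SD solved backwards from the 80% should not be inserted, because that would make the claim circular.
2. State the expected precision for the primary outcome as defined. For a count of products, the 95% CI half-width is 0.75 SD with 15 evaluable per arm or 0.85 SD with 12. For a binary outcome, give the half-width for a difference in proportions at the expected rates, with their source.
3. State screen failure (after consent, before randomisation) and post-randomisation loss as two separate rates. Derive the numbers consented, randomised and evaluable from them, and use these consistently in Human Participants, questions 1 to 4, and Statistical Considerations, question 2.

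The cost is wording only. The allocation and trial procedures do not change; the plan gives up a favourable but unsupported figure.
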